8.3.3 Reporting Procedure

The following process for reporting a SAE ensures compliance with the ICH guidelines and 21CFR §312.32.

REPORTING CRITERIA FROM SPONSOR TO HEALTH AUTHORITY

After the SAE has been assessed, the event will be reported by the IND sponsor to the appropriate health authorities in the required manner based on the following criteria:

No reporting. This requirement applies if the AE is deemed not serious by the University Of Iowa DCC medical reviewer and the PI.

Standard reporting (*i.e.*, must be included in the Investigational New Drug [IND] annual report to the health authorities). This requirement applies if the AE is classified as any of the following:

- Serious, expected, and drug related.
- Serious, expected, and *not* drug related.
- Serious, *unexpected*, and not drug related.

Expedited reporting. This requirement applies if the AE is considered serious, unexpected, and drug related as defined in 21 CFR 312.32. This type of SAE must be reported by the sponsor to the appropriate health authorities within 15 calendar days; fatal or life-threatening events must be reported within 7 calendar days.

REPORTING TIMELINE – FROM THE SITE TO THE UNIVERSITY OF IOWA DCC

When an investigator identifies an SAE, he or she must notify the University Of Iowa DCC Safety Reporting Center within 24 hours of discovering the event by submitting an initial electronic SAE CRF. In the event that the eCRF cannot be submitted (*i.e.* computer failure), the site must fax a paper SAE report to the DCC within 24 hours of discovering the event.

AEs other than SAEs will be reported to the DCC by the sites on at least a monthly basis.

REPORTING TIMELINE – FROM THE DCC TO THE SPONSOR AND HEALTH AUTHORITIES

The DCC is responsible for notifying the sponsor within 2 business days of receiving the report by the clinical site. The sponsor is responsible for disseminating reports to the health authorities, and all investigators in the study. SAEs per 21 CFR 312.32 definitions, except elective hospitalizations, will be reported to the Health Authority by the IND sponsor in accordance with applicable regulations.

NOTIFYING THE DATA AND SAFETY MONITORING BOARD

The DCC will provide the DSMB with listings of all SAEs on an ongoing basis, and at least yearly.

NOTIFYING THE INSTITUTIONAL REVIEW BOARD AND ETHICS COMMITTEE

The investigator will ensure the timely dissemination of SAE information, including expedited reports, to the IRB and Ethics Committee (EC) in accordance with applicable regulations and guidelines.

REPORTING PREGNANCY AS A SERIOUS ADVERSE EVENT

Any pregnancy that occurs during a clinical study that is using an investigational drug must be reported to the DCC utilizing the SAE report form. This report is *for tracking purposes only*. All pregnancies that are identified during the study must be followed to conclusion and the outcome of each must be reported. The investigator should report all pregnancies within 24 hours using the SAE report form. The investigator should counsel the subject and discuss the risks of continuing with the pregnancy and the possible effects on the fetus. A woman who becomes pregnant or wishes to while on the study will be counseled as to her choices and will be encouraged to discuss those choices with her obstetrician. Monitoring of the subject should continue until the conclusion of the pregnancy, and a follow-up SAE report form detailing the outcome of the pregnancy should be submitted to the DCC.

8.3.4 Updating Source Documentation

Documents describing the safety profile of a drug, such as the investigator's brochure, will be amended as needed by the study drug manufacturer to ensure that the description of safety information adequately reflects any new clinical findings. The Investigator's Brochure for the islets will be amended as needed by the IND sponsor. Until these documents are updated, expedited reporting will be required for additional occurrences of a reaction.

9. MECHANISTIC ASSAYS

Time points are listed relative to each islet transplant; therefore the clock is restarted with each subsequent transplant. Exceptions are noted in each respective section. For logistical purposes, the day 75 time point is equivalent to the 3 month evaluation.

9.1 Metabolic Testing

The timing of all assessments is provided in the Schedule of Events (Appendix 1).

9.1.1 Insulin Requirement

Subjects will record their daily insulin dose on self-monitoring diaries. Subjects should be given exogenous insulin as needed to maintain fasting capillary glucose level ≤ 140 mg/dL at a minimum of 4 out of 7 days per week; 2-hour post-prandial capillary glucose levels should not exceed 180 mg/dL more than 3 times per week. Average daily insulin requirements will be obtained. It will also be determined if the subject achieved the targeted level of metabolic control (HbA1c $\leq 6.5\%$).

9.1.2 Glycemic Control

Glycemic control will be assessed by HbA1c (%) which will be analyzed by local labs at each center.

9.1.3 Glycemic Lability

Glycemic lability will be assessed by both the MAGE¹³⁴ and the LI¹²⁹.

The MAGE requires 14 – 16 capillary BG measurements over two consecutive days taken before and 2 hours after breakfast, lunch, and dinner, and at bedtime with an optional measurement at 3 AM. A glycemic excursion is calculated as the absolute difference in peak and subsequent nadir (or vice versa) glucose values, with the direction (peak to nadir versus nadir to peak) determined by the first quantifiable excursion in the two day period. All excursions > 1 S.D. of the 7 – 8 glucose readings for the day in which they occurred qualify for the analysis, where they are summed and divided by the number of qualified excursions to give the MAGE in mg/dL glucose. A MAGE > 200 mg/dL is indicative of marked glycemic lability.

The LI requires 4 or more daily capillary BG measurements over a 4 week period and is calculated as the sum of all the squared differences in consecutive glucose readings divided by the hours apart the readings were determined (range 1 to 12 hours) in (mmol/L²/hr·wk⁻¹). A LI greater than or equal to the 90th percentile (433 mmol/l²/hr·wk⁻¹) of values derived from an unselected group of T1D subjects is evidence for severe glycemic lability.

9.1.4 Hypoglycemia

Episodes of severe hypoglycemia will be documented as defined by an event with one of the following symptoms: memory loss; confusion; uncontrollable behavior; irrational behavior; unusual difficulty in awakening; suspected seizure; seizure; loss of consciousness; or visual symptoms, in which the subject was unable to treat him/herself and which was associated with either a BG level < 54 mg/dL or prompt recovery after oral carbohydrate, IV glucose, or glucagon administration⁷.

In addition, composite indices of hypoglycemia frequency, severity, and symptom recognition will be assessed by both the Clarke survey¹³² and the HYPO score¹³³.

The Clarke survey involves subject completion of eight questions scored by the investigator according

to an answer key that gives a total score between 0 and 7 (most severe), where scores of 4 or more indicate reduced awareness of hypoglycemia and increased risk for severe hypoglycemic events.

The HYPO score involves subject recording of BG readings and hypoglycemic events (BG <54 mg/dL) over a 4-week period and recall of all severe hypoglycemic episodes in the previous 12 months. A HYPO score greater than or equal to the 90th percentile (1047) of values derived from an unselected group of T1D subjects indicates severe problems with hypoglycemia.

9.1.5 Mixed-Meal Tolerance Test

Basal (fasting) and stimulated glucose and c-peptide levels will be determined using the MMTT. Subjects will be instructed not to eat or inject short-acting (or bolus) insulin after 8 PM the night before the test. Evening or bedtime administration of long-acting insulin will be permitted, as will consumption of water. Subjects receiving CSII may remain on the basal rate of insulin.

Subjects will arrive fasting to the transplant or diabetes clinic where the capillary BG will be checked. If the BG is ≤ 70 mg/dL or ≥ 180 mg/dL, the test will be rescheduled for the next possible day. If the BG is 70 – 180 mg/dL, basal glucose and c-peptide levels will be drawn. Immediately after, the subject will receive 6 mL per kg BW (to a maximum of 360 mL) of Boost® High Protein Drink (or a nutritionally equivalent substitute) to consume in 5 minutes starting at time = 0. Then, at time = 60 and 90 minutes, stimulated glucose and c-peptide levels will again be drawn.

Each blood sample collected for c-peptide and glucose determination will be drawn and processed according to the local site's guidelines.

9.1.6 B-Score: A Composite Index of Post-transplant Graft Function

The β -score will be determined from the HbA1c, insulin requirements, fasting (basal) serum glucose, and basal or stimulated c-peptide as developed by Ryan et al¹²⁹. The score may range from 0 (no graft function) to 8, with all subjects reported with a score of 8 also having 90-minute serum glucose levels during a MMTT that are ≤ 180 mg/dL, indicative of excellent graft function.

9.1.7 The C-peptide to Glucose, Creatinine Ratio

The c-peptide to glucose, creatinine ratio (CPGCR) will be determined using the fasting (basal) serum glucose and c-peptide, and a simultaneous SCr. This measure accounts for both the dependence of c-peptide secretion on the ambient glucose concentration and the dependence of c-peptide clearance on kidney function^{138,139}. The CPGCR is calculated as $[\text{c-peptide (ng/mL)} * 100]/[\text{glucose (mg/dL)} * \text{creatinine (mg/dL)}]$. An index of islet graft function, this measure correlates well with both the 90-minute serum glucose levels during a MMTT and with the β - score.

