3. SELECTION AND WITHDRAWAL OF SUBJECTS

3.1 Inclusion Criteria

Subjects who meet *all* of the following criteria are eligible:

1. Male and female subjects age 18 to 70 years.
2. Subjects who are able to provide written informed consent and to comply with the procedures of the study protocol.
3. Subjects in the United States must have one of the following payment mechanisms in place:
 - a. Medicare,
 - b. A third-party insurer who agrees, via pre-authorization, to pay for participation in the study, or
 - c. Another mechanism of payment (self-pay, hospital, university, donations, etc.) for participation in the study.
4. Clinical history compatible with T1D with disease onset < 40 years of age and insulin-dependence for ≥ 5 years at the time of enrollment.
5. Absent stimulated c-peptide (< 0.3 ng/mL) in response to a MMTT [Boost[®] 6 mL/kg body weight (BW) to a maximum of 360 mL; another product with equivalent caloric and nutrient content may be substituted for Boost[®]] measured at 60 and 90 min after start of consumption.
6. Subjects who are ≥ 3 months post-renal transplant who are taking appropriate calcineurin inhibitor (CNI) based maintenance immunosuppression ([tacrolimus alone or in conjunction with sirolimus, mycophenolate mofetil, myfortic, or azathioprine; or cyclosporine in conjunction with sirolimus, mycophenolate mofetil, or myfortic] \pm Prednisone ≤ 10 mg/day).
7. Stable renal function as defined by a creatinine of no more than one third greater than the average creatinine determination performed in the 3 previous months prior to islet transplantation, until rejection, obstruction or infection is ruled out.
8. Subjects who meet one of the options in the following criterion are eligible for transplantation:
 - Reduced awareness of hypoglycemia manifested by a Clarke score of 4 or more measured upon study enrollment and at least one episode of severe hypoglycemia in the 12 months prior to study enrollment.

OR

 - a subject must have a reduced awareness of hypoglycemia manifested by a Clarke score of 4 or more and at least 1 episode of severe hypoglycemia;

OR

 - Any subject not meeting the hypoglycemia option must have an HbA1c $\geq 7.5\%$.

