- HbA1c comparing GLASSIA treated versus control CIT-06 subjects at 1 year and 2 years following the *first* and *last* islet transplant(s)

Glycemic Control

- The change in Clarke score from baseline in GLASSIA treated versus control CIT-06 subjects at:
 - 1 year after the first islet transplant.
 - 2 Years after the first islet transplant
- β -score comparing GLASSIA treated versus control CIT-06 subjects at 1 year and 2 years following the *first* and *last* islet transplant(s)
- Glucose variability and hypoglycemia duration derived from the CGMS comparing GLASSIA treated versus control CIT-06 subjects at 1 year and 2 years following the first and last islet transplant(s)
- Basal (fasting) and 90-min glucose and c-peptide derived from the mixed-meal tolerance test (MMTT) comparing GLASSIA treated versus control CIT-06 subjects at 1 year and 2 years following the first and last islet transplant(s)
- MAGE comparing GLASSIA treated versus control CIT-06 subjects at 1 year and 2 years following the first and last islet transplant(s)
- Glycemic lability index (LI) comparing GLASSIA treated versus CIT-06 control subjects at 1 year and 2 years following the first and last islet transplant(s)
- Ryan hypoglycemia severity (HYPO) Score comparing GLASSIA treated versus control CIT-06 subjects at 1 year and 2 years following the first and last islet transplant(s)
- C-peptide: (glucose· creatinine) ratio (CPGCR) comparing GLASSIA treated versus control CIT-06 subjects at 1 year and 2 years following the first and last islet transplant(s)
- Rate of favorable outcome at each center preparing islets (rate of subjects with HbA1c \leq 6.5% and absence of severe hypoglycemic events from Day 28 to Day 730, or reduction in HbA1c of 1 point and absence of severe hypoglycemia from Day 28 to Day 730).

Repeat Transplants

- The proportion of subjects receiving a second islet transplant comparing GLASSIA treated versus control CIT-06 subjects at 1 year and 2 years following the first and last islet transplant(s)
- The proportion of subjects receiving a third islet transplant comparing GLASSIA treated versus control CIT-06 subjects at 1 year and 2 years following the first and last islet transplant(s)

Other Efficacy Endpoints

- Cardiovascular events [death, cerebrovascular accident (CVA), myocardial infarction (MI)] and changes in atherogenic profile for GLASSIA treated versus control subjects at 1 year and 2 years following the first and last islet transplant(s)

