Most of the secondary endpoints are measured before transplant, at day 75 (A1c, MMT, FSIGT, MAGE, c-peptide and Beta score) and at one year post-initial transplant (HbA1c, fasting and 90 minute MMTT, c-peptide, glucose, and c-peptide glucose creatinine ratio, MAGE, HYPO, Clarke survey, and Beta score). We will compare these markers with those in the CIT-06 controls using student's t-test, nonparametric test (e.g., Mann-Whitney U test, Wilcoxon signed rank test), or chi-square test when appropriate. A pre-post analysis will be used for these variables. For continuous variables that are normally distributed or that can be transformed to a normal distribution, we will compute an appropriate estimate and 95% confidence interval for the mean change and a paired t-test for testing that the mean change is zero. If an appropriate normalizing transform cannot be identified then a signed-rank test will be used to test for a significant change. Similarly, a McNemar test will be used to test for a significant change for dichotomous outcome variables.

For those continuous secondary endpoints that are only observable after transplantation or for whom

change from baseline are not meaningful we will compute estimates of the mean and 95% confidence intervals. Similarly, for binary endpoints we will compute the observed rates and exact 95% confidence intervals. Levels of these markers will be compared with those in the CIT-06 controls using student's t-test or nonparametric test (e.g., Mann-Whitney U test) when appropriate.

Regression models for continuous longitudinal data (mixed models) will be used to describe the profiles of change over time for each of the response variables where measurements are repeated over time. Similar models will be used to model dichotomous variables over time.

Survival analysis models will be used to compare time to becoming insulin dependent and to identify risk factors through Kaplan-Meier estimates and Cox regression models.

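### Stimulated (90-minute MMTT) c-peptide is compared with the non-randomised CIT-06 cohort without a renal term, although the protocol itself says c-peptide clearance depends on kidney function

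*Combined protocol and SAP*

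**What the plan says.** Section 4.1.2 lists among the secondary endpoints "Basal (fasting) and 90-min glucose and c-peptide derived from the mixed-meal tolerance test (MMTT) comparing GLASSIA treated versus control CIT-06 subjects", at 1 and 2 years after the first and last transplant. The CPGCR is listed separately, against the same controls and at the same times.

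Section 9.1.7 defines the CPGCR as fasting c-peptide × 100 divided by the product of fasting glucose and simultaneous creatinine, and justifies it by "the dependence of c-peptide secretion on the ambient glucose concentration and the dependence of c-peptide clearance on kidney function". No such correction is given for the 60- or 90-minute sample.

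Section 10.1.2 gives the between-cohort method: "We will compare these markers with those in the CIT-06 controls using student's t-test, nonparametric test" or chi-square. For endpoints seen only after transplant it says: "Levels of these markers will be compared with those in the CIT-06 controls using student's t-test or nonparametric test". Neither sentence names a covariate. The mixed models in that section "will be used to describe the profiles of change over time for each of the response variables"; no cohort contrast or renal term is attached to them.

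Section 7.8.1 states that the study is open-label and non-randomised. The demographic variables named in Section 10.2.1 do not include renal function, and Section 10.2.4 leaves the presentation of renal change to a later SAP.

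**The concern.** Every subject has a kidney allograft, so variation in renal function is built into this population. The entry criteria are said in Section 4.1 to derive from CIT-06, but on renal function they set only a GFR floor (40, or 35 for vegans) and a within-subject stability rule. Two cohorts can both satisfy them and still differ in mean creatinine.

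A cohort with slower c-peptide clearance would show higher stimulated c-peptide for the same islet secretion. Stimulated c-peptide is a fairly direct readout of engrafted function, which is the trial's thesis. A renal difference could therefore mimic an AAT effect, hide one, or look like harm.

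The planned pre-post analysis does not remove this. Inclusion criterion 5 requires stimulated c-peptide below 0.3 ng/mL "in response to a MMTT" before transplant, so the change from baseline is nearly the post-transplant value itself and carries the same clearance effect.

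**Working it through.** **Inputs from the documents.** c-peptide mean 2, SD 0.7, 95% half width 0.31 (Table 9, Section 10.3.2; it does not say whether fasting or stimulated); 20 GLASSIA subjects (Section 10.3.1); 24 CIT-06 subjects (Section 1.1).

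**Assumptions.** Two-sided 5% level (none is stated for secondary comparisons; the planned intervals are 95%). Equal islet secretion in both cohorts. Creatinine higher in GLASSIA by a stated percentage, since no creatinine values are given for either cohort. c-peptide either proportional to creatinine (the form of the CPGCR) or half as responsive, since Section 9.1.7 gives no size for the dependence.

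**Plan's own figure.** 1.96 × 0.7 / √20 = 0.307, which rounds to 0.31. Table 9 is reproduced.

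**Between-cohort precision.** SE = 0.7 × √(1/20 + 1/24) = 0.212 ng/mL; 95% half width with 42 df = 0.43 ng/mL.

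**False positives of the unadjusted t-test** (noncentral t, 42 df; shift = 2 × creatinine difference × slope):

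| Creatinine difference | Proportional: shift, rejection | Half strength: shift, rejection |
|---|---|---|
| 10% | 0.20 ng/mL, 15.2% | 0.10 ng/mL, 7.5% |
| 20% | 0.40 ng/mL, 45.4% | 0.20 ng/mL, 15.2% |

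With creatinine lower in GLASSIA the same rates apply in the opposite direction.

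**Effect of adjusting.** A log-scale simulation (4,000 runs per scenario, creatinine CV 25% assumed, no AAT effect) compared three analyses at creatinine differences of 0, 10, 20 and 30%:

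- The raw t-test rejected in 5, 15, 40 and 68% of runs under proportionality, and in 5, 7, 14 and 23% at half strength.
- A model adjusted for log creatinine stayed at 4-6% throughout.
- Dividing c-peptide by creatinine held about 5-6% under proportionality, but rejected in 5, 7, 13 and 23% at half strength. Extending a simple ratio to the 90-minute value is therefore not a safe substitute for a fitted covariate.

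The simulated covariate is the creatinine that acts on the c-peptide sample. A pre-transplant value removes bias only so far as it tracks creatinine at sampling. No failed grafts were simulated.

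**Precision gain.** R² = (2 × slope × CV)² / 0.49, and the gain is 1/(1 − R²). For assumed creatinine CVs of 15, 20 and 25%:

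- Proportional: R² = 18, 33 and 51%; gain 1.2, 1.5 and 2.0 times the sample size.
- Half strength: R² = 4.6, 8.2 and 12.8%; gain 1.05, 1.09 and 1.15 times.

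**The case against.** **No renal difference is shown.** The false-positive rates need a systematic difference. Chance imbalance is already inside the nominal 5%, and the simulation gives 5% when there is no systematic difference. At creatinine CVs of 15-25% the SE of the cohort difference is CV × √(1/20 + 1/24) = 4.5-7.6%, so a 20% difference is 2.6 to 4.4 standard errors and would mean that the populations really differ. Shared entry criteria make that less likely. This stands: a reader might infer that the comparison will show a spurious AAT effect, and the documents do not support that. They show only that nothing in the planned analysis would detect or remove a difference.

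**Fasting c-peptide is largely covered.** The CPGCR comparison runs at the same time points. This stands, and the gap is confined to the stimulated value.

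**FSIGT.** A reader might extend the point to the islet-mass endpoint. Sections 4.1 and 10.1.1 speak of an AUC for insulin secretion and do not say that it is derived from c-peptide, so the extension is conjecture.

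**Limited consequence.** This is one of many secondary endpoints. Section 10.1.2 already warns that significant secondary findings may be type 1 errors, and Section 10.1.3 also lists c-peptide for descriptive statistics. A reader might think the primary endpoint is compromised, but in the definition of insulin independence c-peptide is a single threshold (at least 0.5 ng/mL, fasting or stimulated) among several criteria. Its exposure is small.

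**A log-scale ANCOVA alone is inadequate.** Graft failure is defined by c-peptide below 0.3 ng/mL, and near-zero values would dominate a log analysis. The rank test in the plan tolerates them. This stands and shapes the fix. In addition, Appendix 2 lists no MMTT or c-peptide on reduced follow-up, so some failed grafts may be absent from the comparison altogether; renal adjustment does not address that.

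**Which creatinine.** Clearance acts at sampling, which favours the same-visit value. That value is post-treatment, and Section 9.1.10 studies it as an outcome. Neither choice is clean, so both should be reported.

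**Conclusion.** The concern holds for 90-minute MMTT c-peptide. The protocol states the renal dependence, corrects for it only in the fasting index, and leaves the stimulated value to an unadjusted comparison of non-randomised cohorts.

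The size is conditional. It rests on an assumed systematic creatinine difference, on a dependence between half-strength and proportional, and on applying the Table 9 figures to the stimulated value. On those terms two-sided false positives are about 7.5-15% at a 10% difference and 15-45% at 20%, and the bias can run either way. The precision benefit ranges from negligible (1.05 times) to substantial (2.0 times); the upper figure needs both proportionality and a creatinine CV of 25%, so it should not be quoted alone.

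This is worth correcting because it is cheap, but it does not threaten the primary analysis.

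**What to change.** In Section 10.1.2, prespecify for 90-minute MMTT c-peptide:

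- A regression on cohort adjusted for log creatinine or CKD-EPI eGFR, with the last pre-transplant value as primary covariate and the same-visit value as a sensitivity analysis.
- Either a log scale with a stated floor for undetectable or failed-graft values, or a rank-based ANCOVA.
- The unadjusted test kept as descriptive.
- A table of creatinine and eGFR by cohort, so that readers can see whether a difference exists.

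Read raw fasting c-peptide alongside the CPGCR. Make no corresponding change for FSIGT unless its AUC turns out to be taken from c-peptide.

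No new measurements are needed in this trial: creatinine is in the metabolic panel (Appendix 1), and Section 4.1 indicates that the CPGCR and renal measures were collected in CIT-06. Access to pre-transplant creatinine for those controls should be confirmed. The cost is one degree of freedom and slightly more analysis work on a secondary endpoint.
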